##### 10.3.4.2 TEST-RETEST RELIABILITY

Participants will undergo cognitive testing with both the Linus Platform tests and the reference standard RBANS twice, where the second examination will be three to five weeks after the first examination. Test-retest reliability of both individual Linus Platform tests and the combined Linus score will be

compared to the test-retest reliability of the RBANS. For the analysis, participants who no longer satisfy the inclusion/exclusion criteria prior to the second examination will be excluded.

For, the individual Linus Platform scores, the developed Linus score, and the reference standard RBANS, agreement analyses will be carried out as follows:

- Agreement between the first and second measurements will be measured. A scatter plot of measurement 2 vs. measurement 1 will be generated, superimposed with a line of identity. An unweighted Deming regression (where the variance of the measurement error is determined by the two measurements that were collected 3-5 weeks apart) will be carried out to determine the y-intercept, slope and their two-sided 95% confidence intervals. The correlation coefficient will also be determined.
- A hypothesis test of the slope vs. 1 and of the y-intercept vs. 0 will be carried out. Specifically, the following hypothesis test will be carried out:

$$H_0: \beta_0 = 0 \text{ vs. } H_1: \beta_0 \neq 0 \text{ and } H_0: \beta_1 = 1 \text{ vs. } H_1: \beta_1 \neq 1$$

where  $\beta_0$  and  $\beta_1$  are the y-intercept and slope, respectively, from the Deming unweighted regression.

#### 10.3.5 SAFETY ANALYSES

Safety analysis will be performed on the DCTclock and Linus Platform safety analysis dataset. Treatment emergent adverse events, which are events that started or worsened during or after the first DCTclock or Linus Platform test, will be listed including start date of event and date and time of the test. The number of serious device related adverse events and number and percentage of subjects with at least one serious device related adverse event will be presented for each test.

#### 10.3.6 PLANNED INTERIM ANALYSES

There is no formal interim analysis for the study. Enrollment and screening results will be reviewed routinely to ensure subjects with a range of cognitive function are represented in the study population.

##### 10.3.6.1 EFFECTIVENESS REVIEW

There will be no review of effectiveness at the interim.

##### 10.3.6.2 SAFETY REVIEW

Testing with the study agent will be halted when three severe AEs determined to be “probably related” are reported to the sponsor. The study sponsor will notify investigators immediately when the third grade 3 event is reported, and enrollment screens will stop accepting new study participants. The study sponsor will inform the FDA of the temporary halt and the disposition of the study. Given the low risk nature of the product, there will be no formal data safety monitoring board (DSMB) but there will be a safety Medical Monitor for the study.

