## 2.3 POTENTIAL RISKS AND BENEFITS

### 2.3.1 KNOWN POTENTIAL RISKS

#### DCTclock

DCTclock-pen is a class II, 510(k) exempt medical device and has been used in research and clinical settings with no reported adverse events. DCTclock's validation study (11) had the following safety outcome:

435 participants took a total of 841 DCTclock tests during the DCT032 study. A total of 37 adverse events (AE) were recorded in this population. The percentage of participants experiencing an AE during the study window (1-4 weeks) is not unexpected given that the study included an older population aged 55 to 95 years old. Of the total 37 AEs, only 1 was a serious adverse event (SAE). The SAE was reviewed by the study medical monitor and found to be unrelated to the protocol or study device. There were no reported unanticipated adverse device effects and no reported serious device related AEs.

The 36 non-serious AEs were reviewed by the study Adverse Event Review Team and found to be unrelated to the study device. The most frequent AEs reported were colds and gastrointestinal upset and both occurred in less than 1 percent of participants (4 in 435).

DCTclock-tablet differs from DCTclock-pen predominantly in the use of an Apple iPad and Apple Pencil instead of the digitizing ballpoint pen and paper. It is reasonable to assume that the risk level for DCTclock-tablet will be minimal and the risk profile will be similar to that seen with DCTclock-pen.

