### 8.2 CLASSIFICATION OF AN ADVERSE EVENT

#### 8.2.1 SEVERITY OF EVENT

For all AEs, the following guidelines will be used to describe severity.

- **Mild** – Events require minimal or no treatment and do not interfere with the participant's daily activities.
- **Moderate** – Events result in a low level of inconvenience or concern with the therapeutic measures. Moderate events may cause some interference with functioning.
- **Severe** – Events interrupt a participant's usual daily activity and may require systemic drug therapy or other treatment. Severe events are usually potentially life-threatening or incapacitating.

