#### 8.2.2 RELATIONSHIP TO STUDY AGENT

The clinician's assessment of an AE's relationship to the study device is part of the documentation process, but it is not a factor in determining what is or is not reported in the study. If there is any doubt as to whether a clinical observation is an AE, the event should be reported. All AEs must have their relationship to study agent assessed. In a clinical trial, the study product must always be suspect. To help assess, the following guidelines are used.

- **Related** – The AE is known to occur with the study agent, there is a reasonable possibility that the study agent caused the AE, or there is a temporal relationship between the study agent and event. Reasonable possibility means that there is evidence to suggest a causal relationship between the study agent and the AE.
- **Not Related** – There is not a reasonable possibility that the administration of the study agent caused the event, there is no temporal relationship between the study agent and event onset, or an alternate etiology has been established.

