10.1 PRIMARY SAFETY VARIABLE

The study's primary safety endpoint is the incidence of subjects with serious device-related adverse events from enrollment to completion of the study. Safety will be analyzed on the Safety Population.

A table of treatment emergent adverse events (TEAEs), which are events that started or worsened during or after the first DCTclock or Linus Platform test, will be created. This table will present the number of TEAEs and the number and percent of subjects with at least one TEAE in each visit category (visit 1, between visits, visit 2, or at any time) with which the TEAE is associated.

TEAES will be categorized as follows at each visit, with the number of TEAEs and number and percent of subjects with at least one TEAE presented for each category at each visit:

- Any TEAE,
- TEAE by severity (mild/moderate/severe; if a subject has more than one TEAE, then only the events in the most severe category experienced will be tabulated, and the subject will be placed in the most severe category experienced),
- Relationship (not related or related, where related is further broken down by the categories of possible, probable, definite) to each of the following (if a subject has more than one TEAE, then only the events in the most related category experienced will be tabulated, and the subject will be placed in the most related category experienced):
 - DCTclock-pen (the denominator at Visit 1 and between visits will be those subjects who underwent testing with the pen at Visit 1; the denominator at Visit 2 will be those subjects who underwent testing with the pen at Visit 2)
 - DCTclock-tablet/drawing tests,
 - Decision making/reaction time,
 - Balance/walking,
 - PHQ-9/Lifestyle questionnaire (Visit 2 only),
 - Speech elicitation assessments,
 - Eye tracking assessments (Visit 2 only),
 - Other study assessments,
 - Concomitant medication,
 - Intercurrent intervention/procedure,
 - Pre-existing condition/underlying disease,
 - Intercurrent condition,
 - Incidental finding,
 - Unknown,
 - Other.
- Whether the TEAE led to study discontinuation or not,
- Whether the TEAE is a serious adverse event (SAE or not),
- Whether the TEAE led to death or not.

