TEAEs will also be presented in a listing. This listing will include the randomization group, site, subject ID, visit number, date of visit, date of TEAE onset, study day number of onset, date TEAE resolved, number of study days from start to resolution of TEAE, whether it is an SAE or not (if so the reasons for the SAE will be listed after 'Y' in the SAE column), whether or not the study resulted in study discontinuation, outcome, severity, relationship to any study device/test component (any instance in which the TEAE is at least possibly related will be listed and in parentheses will be the exact noted relationship i.e. balance/walking (probable)) and action taken (in any instance in which

the action taken requires a specification, the specification will be written in parentheses i.e. medication (Ativan)).

A listing for device observations (observations associated with the Linus Platform devices) will be presented. This listing will display the randomization group, site, subject ID, description of the observation, observation #, date and study day of observation, whether or not the observation is related to an AE, whether or not the observation is related to Linus platform device components (and if so, which one(s)), time the observation occurred, type of observation, action taken to address the observation/outcome.

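### The safety halt counts severe AEs that are 'probably related', a level protocol 8.2.2 does not define and one that, taken literally on the SAP scale, leaves out definite events

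*Protocol*

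**What the plan says.** **Protocol 10.3.6.2 (Safety Review)** sets the trigger: "Testing with the study agent will be halted when three severe AEs determined to be" probably related are reported to the sponsor. It then continues: "The study sponsor will notify investigators immediately when the third grade 3 event is reported, and enrollment screens will stop accepting new study participants".

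**Protocol 8.2.1 (Severity of Event)** introduces its scale with "For all AEs, the following guidelines will be used to describe severity" and gives three named levels: mild, moderate and severe. It has no numeric grades.

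**Protocol 8.2.2 (Relationship to Study Agent)** requires that "All AEs must have their relationship to study agent assessed" and gives two categories, Related and Not Related. Besides events already known to occur with the study agent, an AE is Related if "there is a reasonable possibility that the study agent caused the AE, or there is a temporal relationship between the study agent and event".

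**SAP 10.1 (Primary Safety Variable)** uses a finer scale, "where related is further broken down by the categories of possible, probable, definite". Its listing of treatment-emergent events keeps that detail: "any instance in which the TEAE is at least possibly related will be listed and in parentheses will be the exact noted relationship".

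**Other safeguards.** Protocol 5.5 allows suspension for unacceptable risk, with no count attached. Protocol 8.5 provides a Medical Monitor, who reviews events under an AE/SAE Handling Plan, and states that there is no DSMB.

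**The concern.** A halt rule should give one answer when it is applied to a given set of events, and the wording should be settled before any event occurs. Here the person keeping the count has a relationship term that the protocol's causality section does not contain. An investigator who follows 8.2.2 exactly can return Related or Not Related, and neither tells the sponsor whether the event counts.

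The SAP scale does contain a matching word, but it places definite above probable as a separate level. The rule does not say 'at least', so its literal wording leaves out the events with the strongest evidence of device causation. That is the wrong direction for a safety threshold.

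The second sentence adds a smaller uncertainty. It uses a different severity term and drops the relationship term, so the trigger for notice and the enrollment stop is not worded the same way as the trigger for the halt.

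**Working it through.** The threshold of three is stated without an event rate or an error probability, so there is no planned figure to reproduce. The check is a comparison of the texts, followed by applying the rule to example events.

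**1. The terms side by side**

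| Place | Severity term | Relationship term |
|---|---|---|
| Protocol 10.3.6.2, halt sentence | severe | probably related |
| Protocol 10.3.6.2, notice sentence | grade 3 | none |
| Protocol 8.2.1 | mild, moderate, severe | not covered |
| Protocol 8.2.2 | not covered | Related, Not Related |
| SAP 10.1 | mild, moderate, severe | not related; related as possible, probable or definite |

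The severity term in the halt sentence has a match in 8.2.1. The relationship term has no match in 8.2.2. It has one in the SAP, but nothing in either document says that the halt rule uses the SAP scale or that definite events are included.

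**2. The rule applied on the SAP scale**

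Count = number of severe AEs whose relationship is in the counted set; halt if the count is at least 3.

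| Three severe AEs | Count, literal (probable only) | Count, at least probable |
|---|---|---|
| 3 probable | 3, halt | 3, halt |
| 2 probable, 1 definite | 2, no halt | 3, halt |
| 1 probable, 2 definite | 1, no halt | 3, halt |
| 3 definite | 0, no halt | 3, halt |

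Any set of three that includes a possible event fails to halt under both columns. The two readings therefore differ exactly when the three events are all probable or definite and at least one is definite. This shows where the wording matters; it says nothing about how often such sets would arise.

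**3. How rare the trigger is (illustration only)**

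- Input: Protocol 2.3.1 describes the pen validation study in 435 participants. "A total of 37 adverse events (AE) were recorded in this population", and all 37 were judged unrelated to the device (1 serious, 36 non-serious). That is 0 of 435 participants with a device-related AE.
- One-sided 95% upper limit for the rate: 1 − 0.05^(1/435) = 0.00686, or 0.69% per participant.
- Assumed share of such events that are severe: 5%, 10% or 20% (not in the documents). Rates: 0.00686 × 0.05 = 0.000343; × 0.10 = 0.000686; × 0.20 = 0.00137.
- Chance of at least three participants with such an event among the 200 planned, Binomial(200, rate): 0.005%, 0.04% and 0.28%.

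These figures do not bound this study. The pen study's window was 1–4 weeks, its protocol summary mentions no gait tasks, and its reviewers may not have applied the timing criterion in 8.2.2. The figures indicate only that a halt on device-related severe events is unlikely.

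**The case against.** The strongest reply is that the scales are nested. The SAP subdivides related, its listing reports the exact level noted, and the SAP states that the CRFs were consulted in preparing it. The level is therefore probably recorded for each event, and what is missing is a cross-reference. A clinician would read the rule as at least probably related; no sponsor would disregard three severe, definitely device-caused events. Much of this stands, and it is why the point is minor. It does not remove the mismatch: the CRF is not among the documents, 8.2.2 still offers two categories, and the words 'or definitely' are absent.

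The AE/SAE Handling Plan may also fix the scale on which events are adjudicated. If so, the count may be unambiguous in practice, although the mismatch within the protocol would remain. The plan cannot be seen here.

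Two stronger readings are tempting, and the documents do not support them:

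- **That three severe AEs with only a possible or temporal link would halt the study, because 8.2.2 calls them Related.** This replaces the words of 10.3.6.2, which say probably related. Section 8.2.2 also classes an event as Not Related when another cause has been established, so timing does not always decide.
- **That the grade 3 sentence is a separate trigger regardless of relationship.** Severe is the third of three levels in 8.2.1 and the sentence directly follows the three-event rule, so the same events are the natural reading.

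**Conclusion.** The point holds as a wording defect in a safety rule, of minor severity. The protocol's one numeric halt threshold depends on a relationship level that its own scale cannot assign. On the SAP scale the literal text excludes definite events, so three severe definite AEs count as 0 instead of 3. The grade 3 wording is undefined, although its meaning can be inferred.

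The practical effect is small. Severe device-related AEs are expected to be rare, Medical Monitor review and discretionary suspension continue, an investigator may end an individual's participation (protocol 5.4.1), and SAEs must be reported within 24 hours (protocol 8.4). A reader might infer that participants are unprotected, or that the chance of a halt varies widely with the reading. Neither follows. The documents give no rate of severe AEs by relationship level, so no difference in halt probability between readings can be calculated from them. No endpoint, sample size or analysis is affected.

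The conclusion rests on the text of 10.3.6.2, 8.2.1, 8.2.2 and SAP 10.1. The judgment that the intent was at least probably related is an inference.

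**What to change.** - **Protocol 10.3.6.2:** state that testing is halted, investigators are notified and enrollment stops when the third AE that is severe (as defined in 8.2.1) and probably or definitely related to a study device or test is reported to the sponsor. Delete the reference to grade 3.
- **Protocol 8.2.2:** state that Related is recorded as possible, probable or definite, as in SAP 10.1.

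The cost is one protocol amendment, which needs IRB approval before use (protocol 13.2), and notice to site staff, who are trained on the protocol (7.1). No new data are needed if the CRF already records the three levels, as SAP 10.1 implies. The one substantive consequence is that counting definite events makes a halt slightly easier to reach than under the literal text.

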#### 10.3.7 MULTIPLE COMPARISON/MULTIPLICITY

Given the nature of the analysis, there will be no adjustment for multiple comparisons.

#### 10.4 MEASURES TO MINIMIZE BIAS

**10.4.1 ENROLLMENT/ RANDOMIZATION/ MASKING PROCEDURES**

Blocked randomization of subjects into group 1 and 2 will be used. Subjects will be randomized immediately prior to the visit 1 DCTclock test. A block size of 4 will be used. The allocation ratio will be 1:1 to obtain the same number of subjects per group.

**10.4.2 EVALUATION OF SUCCESS OF BLINDING**

N/A

**10.4.3 BREAKING THE STUDY BLIND/PARTICIPANT CODE**

N/A

**11 SOURCE DOCUMENTS AND ACCESS TO SOURCE DATA/DOCUMENTS**

Each participating site will maintain appropriate medical and research records for this trial, in compliance with regulatory requirements and institutional requirements for the protection of confidentiality of participants. Each site will permit authorized representatives of the sponsor and regulatory agencies to examine (and when permitted by applicable law, to copy) clinical records for the purposes of quality assurance reviews, audits, and evaluation of the study safety, progress, and data validity.

Source data are all information, original records of clinical findings, observations, or other activities in a clinical trial necessary for the reconstruction and evaluation of the trial.

**12 QUALITY ASSURANCE AND QUALITY CONTROL**

QC procedures will be implemented. Any missing data or data anomalies will be communicated to the site(s) for clarification/resolution.

Following written SOPs, the monitors will verify that the clinical trial is conducted, and data are generated, documented (recorded), and reported in compliance with the protocol, GCP, and the applicable regulatory requirements.

The investigational site will provide direct access to all trial related sites, source data/documents, and reports for the purpose of monitoring and auditing by the sponsor, and inspection by local and regulatory authorities.

**13 ETHICS/PROTECTION OF HUMAN SUBJECTS****13.1 ETHICAL STANDARD**

This study will be performed in accordance with the relevant parts of the Code of Federal Regulations, ICH Guidelines for Good Clinical Practice (GCP), the Belmont Report and any other applicable regional and/or national regulations.

**13.2 INSTITUTIONAL REVIEW BOARD**

The protocol, informed consent form(s), recruitment materials, and all participant materials will be submitted to the IRB for review and approval. Approval of both the protocol and the consent form must be obtained before any participant is enrolled. Any amendment to the protocol will require review and approval by the IRB before the changes are implemented to the study. All changes to the consent form

will be IRB approved; a determination will be made regarding whether previously consented participants need to be re-consented.

### 13.3 INFORMED CONSENT PROCESS

#### 13.3.1 CONSENT/ASSENT AND OTHER INFORMATIONAL DOCUMENTS PROVIDED TO PARTICIPANTS

Consent forms describing in detail the study agent, study procedures, and risks are given to the participant and written documentation of informed consent is required prior to any testing.

#### 13.3.2 CONSENT PROCEDURES AND DOCUMENTATION

Informed consent is a process that is initiated prior to the individual's agreeing to participate in the study and continues throughout the individual's study participation. Extensive discussion of risks and possible benefits of participation will be provided to the participants. Consent forms will be IRB-approved, and the participant will be asked to read and review the document. The study staff will explain the research study to the participant and answer any questions that may arise. All participants will receive a verbal explanation in terms suited to their comprehension of the purposes, procedures, and potential risks of the study and of their rights as research participants. Participants will have the opportunity to carefully review the written consent form and ask questions prior to signing. The participants should have the opportunity to discuss the study with their surrogates or think about it prior to agreeing to participate. **The participant will sign the informed consent document prior to any procedures being done specifically for the study.** The participants may withdraw consent at any time throughout the course of the trial. A copy of the informed consent document will be given to the participants for their records. The rights and welfare of the participants will be protected by the site emphasizing to them that the quality of their medical care will not be adversely affected if they decline to participate in this study.

As subjects with varying levels of cognitive impairment will be recruited for this trial, steps will be taken to ensure that a subject's cognitive status does not impact their ability to consent. Several studies have considered and discussed competency and capacity to consent to research among older persons and those with dementia (19) (20). In agreement with those studies, patients with a previously documented MMSE or Montreal Cognitive Assessment (MoCA) score  $\leq 18$  or who receive a score of 18 or less on the MMSE given during screening will be excluded from the study or required to have a legally authorized representative consent to the study.

For participants with a previously documented MMSE or MoCA score  $>18$  or without a historical score, all attempts will be made to ensure that the participant understands the study including asking them three questions about the study after the consent discussion (how many visits are there, how long do the study visits last, and how much will you be paid). A screening MMSE will also be conducted. If, based on an inability to correctly answer these questions, a subject is not capable of providing consent due to their lack of understanding of the study details, they will be excluded from the study unless consent can be obtained from a legally authorized representative. As noted above for those who do consent and progress to screening, an MMSE score  $\leq 18$  on the screening MMSE administered during the study is also exclusionary. Any subject excluded due to the screening MMSE, can be re-enrolled in the study if a legally authorized representative consents.

